**General information**

Please provide information for all items marked "M" (mandatory).

Items marked "O" are optional.

M	Investigator/institution and contact person: [name] Institut Bergonié, Bordeaux, France	
M	IIR Subtype	Non-interventional/Observational
M	Study Title (Full)  A retrospective Study to Determine the Treatment Outcomes of Subjects with Locally advanced/unresectable or Metastatic Solid Tumors with NTRK Fusions	
M	Indication: Solid Tumors	
M	Phase of Study	Observational
M	Country	France
M	Retrospective or prospective study	Retrospective
M	Planned number of sites/ subjects	3750 subjects (up to 10 sites)
M	Blinding & Control	n/a

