**Additional request details**

M	Primary Endpoint/ objective is safety	No
M	Study exploring new combinations, alternative dosing/dosing schedules or new formulations	No

M	Study with clinical pharmacology objectives, including biomarker, pharmacokinetic (PK) or pharmacodynamics (PD) evaluations	No
O	Author	[name], PhD Institut Bergonie Early Phase Trials and Sarcoma Units [name] Phone: [name] Fax: [name] E-mail: [contact]
O	Investigator Operations Manager email	[name], PhD  Head of Clinical Research Unit: [name] Institut Bergonié – Bordeaux Phone :[name] E-mail : [contact]
M	Study support	Financial
M	Study is financially supported by other organizations	No

Rationale and objectives	
O	Please explain why this study is non-blinded (if applicable): This is a retrospective study.
M	Study Type and Design  This multicenter, retrospective study has a primary objective to assess the impact of NTRK gene fusions on the PFS of first-line systemic therapy for the treatment of locally advanced/unresectable or metastatic solid tumors.  Control subjects will be matched based on the characteristics of the NTRK fusion study population to the greatest extent possible.
M	Rationale  The tropomyosin receptor kinase (Trk) receptor family comprises 3 transmembrane proteins referred to as Trk A, B and C (TrkA, TrkB and TrkC) receptors that are encoded by the NTRK1, NTRK2 and NTRK3 genes, respectively. These receptor tyrosine kinases are expressed in human neuronal tissue and play an essential role in the physiology of development and function of the nervous system through activation by neurotrophins. Gene fusions involving NTRK genes lead to transcription of chimeric Trk proteins with constitutively activated or overexpressed kinase function conferring oncogenic potential. These genetic abnormalities have recently emerged as targets for cancer therapy, because novel compounds have been developed that are selective inhibitors of the constitutively active rearranged proteins. Developments in this field are being aided by next generation sequencing methods as tools for unbiased gene fusions discovery. However, the incidence

	of NTRK aberrations in solid tumors is unknown as well as the natural history of NTRK-rearranged tumors.

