4. Subject has received at least one systemic anti-cancer therapy for locally advanced/unresectable or metastatic disease for which there is available outcome information in terms of PFS, or the latter can be estimated based on the subject's records.

5. Subject has tumor material available for immunoscreening (IHC for NTRK gene fusions).

6. Written and voluntary informed consent understood, signed and dated, or a waiver of consent is granted according to French regulations

Subjects who are tested positive by IHC (Pan-Trk IHC testing with mAb EPR17341) will be the subject of molecular assays such as next-generation sequencing (Archer Dx fusion assay) of tumor material [parrafin embedded material]), so that tumor harboring *NTRK1*, *NTRK2* or *NTRK3* gene fusions, is identified properly.

After identification of the NTRK fusion study population, control subjects with locally advanced/unresectable or metastatic solid tumors, who do not have NTRK fusions will be selected in an attempt to closely match NTRK fusion subjects.

M	
Exclusion Criteria
 
The following exclusion criterion should be considered:
 
Subjects who have not yet received or completed at least one systemic anti-cancer therapy for locally advanced/unresectable or metastatic cancer.

M	
Test Treatment(s) (Description)
 
n/a
 
.

O	
Test Treatment(s) or Investigated Treatment(s): Rationale for unusual or novel approaches
 
n/a

M	
Request for Study Drug Supply
 
No

M	
Reference Treatment or Modality/Treatment or Modality of Comparison (Description)

	n/a
--	-----

Safety reporting	
M	Safety reporting (valid for clinical studies only) n/a

Statistical analysis	
O/M	Standard of Reference/Standard of Truth n/a
M	Rationale for selection of a reference treatment n/a
M	Assignment of subjects to study arms or groups (Randomization/Stratification) n/a (this will be a retrospective study)
M	Blinding n/a
M	Concomitant Treatment(s) n/a
M	Primary Outcome Progression-free survival observed with first-line anti-cancer therapy

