	Collection of Treatment Information: 
 
• Prior/current surgical treatments for cancer. 
 
• Dates of surgeries
 
 
 
• Prior/current radiological treatments for cancer. 
 
• Anatomical sites.
 
• Dates of radiation treatments
 
 
 
• First line systemic treatment for locally advanced/unresectable or metastatic cancer: 
 
• Dates of treatment (start, end).
 
• Performance status at the time of first line therapy for treatment of recurrent or metastatic disease.
 
• Treatment outcome (response and response criteria).
 
• Date of progression(s) (progression criteria).
 
 
 
• Other prior/current systemic treatments for cancer. 
 
• Dates of treatment (start, end).
 
• Treatment outcome (response and response criteria).
 
 
 
• Date of progression(s) (progression
 
		X

	
criteria)
 
 
• Date of death (if any) and cause of death
 
 
Collection of NTRK fusion Information:
 
 
• Anatomical biopsy sample site (including blood/urine sample). Date of sampling and setting (initial diagnosis, locally advanced/unresectable or metastatic disease)
 
• Matrix (tumor biopsy, blood, urine)
 
• Tumor histology (from biopsy sample or primary diagnosis)
 
• NTRK fusion in sample. Allele frequency (if available); this information is not applicable for control subjects.
 
• Other relevant mutations or genetic alterations, if available. Allele frequencies (if available)
 
• Test platform (e.g. NGS). Mutations tested (PCR methods) or exons sequenced (sequencing methods).
 
		
			X
M	
Follow-up period
 
n/a
		

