M	
Statistical & Analytical Plan and Methodology
 
The primary objective of this descriptive study is to determine if there are statistically significant differences in PFS to first line systemic therapy between subjects with recurrent/metastatic disease and NTRK fusion versus those without a known NTRK fusion.
 
The two groups will be matched with respect to histological subtype, sex, age (+/-5 years), and pathological tumor-node-metastasis (TNM) stage.
 
The Kaplan-Meier method will be employed for the analysis of PFS. A nonparametric test, such as the log-rank test, based on the Kaplan-Meier estimator for survival curves, will be employed to assess the association between PFS and the presence of NTRK fusion. In addition, predictive modeling, including Cox proportional hazards models with NTRK fusion as a predictor may also be used to estimate the relative risk of the exit-event of subjects with tumors with NTRK fusion versus subjects with tumors without known NTRK fusion. If the data allow it, other types of predictive modeling may also be explored. If the proportionality of hazard assumption fails, then parametric approaches will be used.
		

	
Given the rarity of NTRK fusions among subjects with solid tumors, the sample size for this study will not be driven by powering the study. A post hoc power calculation will be provided. Clinically relevant changes will be defined as increases in median survival times that are greater than 30%, regardless of confidence interval width.
 
An assessment of the impact of certain covariates will be conducted by comparing their associated hazard ratios from the Cox proportional hazard (or parametric model) analysis.
 
Descriptive statistics will be employed to define demographic and treatment outcome, as well as overall frequency of NTRK fusions in the screened population. This will include exploration of potential effects on subject's treatment outcomes of different forms of NTRK fusions and of other genetic alterations.

--	--

Timelines	

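### Neither site nor date of first-line start is specified in choosing controls, so an era or site imbalance can bias the PFS comparison when fusion cases are few

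*Combined protocol and SAP*

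**What the plan says.** The matching rule is in Statistical & Analytical Plan and Methodology: "The two groups will be matched with respect to histological subtype, sex, age (+/-5 years", followed by pathological TNM stage as the fourth and last factor. Two other places describe matching in general terms. Study Type and Design says "Control subjects will be matched based on the characteristics of the NTRK fusion study population to the greatest extent possible". The text after the inclusion criteria says that, once the fusion cases are known, controls "will be selected in an attempt to closely match NTRK fusion subjects". Neither names a variable.

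The source population is wide. General information gives "3750 subjects (up to 10 sites". Inclusion criterion 4 requires one systemic therapy "for which there is available outcome information in terms of PFS, or the latter can be estimated based on the subject's records" and sets no earliest date. The only calendar dates, under Planned Study Timelines, bound enrolment (December 2018 to December 2019), not the start of first-line therapy.

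Under Collection of Treatment Information, the first-line items include start and end dates, performance status, "Treatment outcome (response and response criteria" and progression dates with the criteria used. Neither the regimen nor the imaging interval is listed.

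The primary comparison is a Kaplan-Meier analysis with a log-rank test and no stated strata. A Cox model is optional. NTRK fusion is its only named predictor, and the other covariates are left unnamed.

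**The concern.** PFS in routine practice depends on which therapy was standard when the patient was treated, how often the centre imaged, and which progression criteria it applied. These vary with calendar time and centre. The four matching factors do not address them, so a fusion patient can be paired with a control treated years earlier at another centre.

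Two features of this plan add to the problem. First, controls are picked after the cases are identified, in a retrospective study where every control's outcome already exists, and nothing says which of several eligible controls is used. Second, an increase in median of more than 30% counts as clinically relevant whatever the width of the confidence interval, so a biased point estimate faces no check on precision. What is at stake is whether a PFS difference can be attributed to the fusion.

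**Working it through.** The plan has no figure to reproduce on this point: it states that no sample size was calculated and gives no expected PFS. The calculations below are therefore illustrations. All assume exponential PFS and no NTRK effect.

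**1. Era mismatch**

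Assumed inputs: median PFS 6 months in the older era and 8 months in the recent era. With a share p treated in the recent era, the group median t solves

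p × 2^(−t/8) + (1 − p) × 2^(−t/6) = 0.5

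| Recent share, cases vs controls | Median, cases (months) | Median, controls (months) | Apparent ratio |
|---|---|---|---|
| 70% vs 50% | 7.32 | 6.91 | 1.06 |
| 80% vs 40% | 7.54 | 6.71 | 1.12 |
| 90% vs 30% | 7.77 | 6.52 | 1.19 |
| 100% vs 0% | 8.00 | 6.00 | 1.33 |

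Only the last row passes the plan's 30% threshold. With a larger assumed era effect (6 vs 12 months, ratio 2.0), the first three mixes give 1.16, 1.34 and 1.54. With 6 vs 9 months (ratio 1.5) they give 1.09, 1.18 and 1.28.

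**2. Imaging interval**

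Assumed input: true median 6 months, so λ = ln 2 / 6 = 0.1155 per month and the true mean is 1/λ = 8.66 months. If progression is dated at the next scan, with scans every d months from treatment start, mean observed PFS is d / (1 − exp(−λd)).

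- 6-weekly: d = 42/30.4375 = 1.38 months; 1.38 / (1 − 0.853) gives 9.36 months, a delay of 0.71 months (8% above the true mean).
- 12-weekly: d = 2.76 months; 2.76 / (1 − 0.727) gives 10.11 months, a delay of 1.45 months (17% above the true mean).
- Between schedules: 10.11 / 9.36 = 1.08.

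The 8% difference requires all cases to be on one schedule and all controls on the other. It is also a shift in means, whereas the 30% threshold concerns medians.

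**3. Imbalance by chance alone**

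Assumed inputs: 3,700 patients; fusion prevalence 0.3%, 0.5% or 1% (about 11, 18 or 37 cases); three controls per case; half of all patients in each era, independently of fusion status. The probability that the recent-era share differs by at least 20 percentage points between the groups, from two independent binomials, is:

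- 11 cases, 33 controls: 26%
- 18 cases, 54 controls: 15%
- 37 cases, 111 controls: 3%

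A 20-point difference is the first row of the era table. With few cases it can arise without any link between fusion status and era.

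**The case against.** The strongest reply is that this is not a historical control group. Cases and controls come from the same immunoscreened cohort, so bias requires fusion status to be associated with era or site within the matched sets. The documents do not report such an association. A reader might infer that fusion patients cluster at referral or paediatric units, or in recent years because newer tissue blocks test better. The documents say neither, and clustering by unit would act largely through age and histology, which are matched. That reply stands against any claim of systematic bias. It does not remove chance imbalance or the open choice among eligible controls.

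A second reply is that the wording leaves room: matching as far as possible and unnamed covariates would both allow site or date to be used. That is correct, and it would be wrong to say that the plan excludes them. They are unspecified, and nothing commits to them.

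A third is that the calendar span is not unlimited. Tumour material must be available, PFS must be recorded or estimable, and enrolment ends in December 2019. The accurate statement is that no earliest date is given.

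Finally, the plan calls the study descriptive and not driven by power. It also seeks a statistically significant PFS difference and sets a relevance threshold, so how controls are chosen still matters.

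**Conclusion.** The point holds as a gap in specification. Site and date of first-line start have no stated role in matching, stratification or adjustment, and the choice among eligible controls is open. An imbalance in either can bias the PFS comparison.

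Under the assumed 6- and 8-month era medians the apparent ratio is about 1.06 to 1.19 with partial mismatch. A reader might infer that era alone would produce a clinically relevant difference as the plan defines it. With these medians that needs complete era separation (1.33), and otherwise both a larger era effect and a marked imbalance. The imaging effect is about 8% in mean observed PFS at full separation by schedule.

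The size and direction of any actual bias cannot be derived from the documents. All these figures rest on assumed medians, era mixes, imaging intervals, prevalence and control ratio. The change is worth making because it is cheap and also limits discretion in control selection.

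**What to change.** Keep the four matching factors. Add to Statistical & Analytical Plan and Methodology that, among fusion-negative patients who satisfy them, the controls chosen are those closest in date of first-line start, from the same site where available, and selected without reference to outcome. Report the distribution of start year and site in each group.

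As a sensitivity analysis, where the number of events allows, adjust the Cox model for start date as a single continuous term. Calendar bands would cost several parameters. Because the Cox model is optional and the log-rank comparison would remain unadjusted, the ranking rule does the main work.

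Cost: slightly more matching and analysis work, and one extra parameter in a small model. Start date is already collected, and site is known by design although it is not a listed data item. No fusion case is lost, because the rule only ranks controls who already qualify. One limit remains: site and date are only proxies for regimen and imaging interval, which are not listed for collection, so some confounding through those could persist.

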M	
Primary Study Objective
 
To assess retrospectively the effect of NTRK gene fusions on the progression free survival (PFS) of first-line systemic therapy for the treatment of locally advanced/unresectable or metastatic solid tumors

O	
Secondary Study Objectives
 
 
• To evaluate the frequency of NTRK gene fusions in subjects with locally advanced/unresectable or metastatic solid tumors.
 
• To assess the treatment outcome to first-line anti-cancer therapy in terms of objective response rate (ORR), duration of response (DOR), and overall survival (OS) in subjects with locally advanced/unresectable or metastatic solid tumors with NTRK gene fusions.
 
• To explore possible demographic characteristics prevalent in subjects with locally advanced/unresectable or metastatic solid tumors and NTRK gene fusions.
 
• To explore the frequency and treatment outcome interaction of concomitant genetic alterations.
 
• To look for trends in the data that may suggest relationships between covariates of interest and treatment outcome in subjects with locally advanced/unresectable or metastatic solid tumors harboring NTRK gene fusions.
 

M	
Study operational/organizational aspects
 
This will be a multicenter, retrospective study. Institut Bergonié as the Sponsor of this study, will be responsible for getting regulatory approvals, selecting the investigational sites, capturing study data in an appropriate data base

Population and methods	
M	
Study Population
 
Adult and pediatric patients with locally advanced/unresectable or metastatic solid tumors

M	
Inclusion Criteria (detailed)
 
For inclusion of a subject in the study population, all of the following criteria must be fulfilled:
 
 
1. Age <math>\geq</math> 1 month.
 

2. Subject has/had a histologically or cytologically confirmed diagnosis of solid tumor including but not exclusively: soft tissue sarcoma, BRAF wild type melanoma, KRAS wild-type colorectal cancer, central nervous system, EGFR-wild type non-small cell lung cancer.

3. Subject has locally advanced/unresectable or metastatic disease.

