O	Secondary Outcomes 
 
Frequency of NTRK fusions in subjects with locally advanced/unresectable or metastatic solid tumors.
 
Treatment outcome to first-line anti-cancer therapy in terms of objective response rate (ORR), duration of response (DOR), and overall survival (OS) in subjects with locally advanced/unresectable or metastatic HNSCC with NTRK gene fusions.
 
Demographic characteristics in subjects with locally advanced/unresectable or metastatic solid tumors harboring NTRK gene fusions
 

M	Safety Outcomes n/a
O	Measurement of results (How assessed)

	Data collection (see below)		
M	Visit schedule		
	Activity	Screening	Data Collection for Enrolled Subjects
	ICF, Inclusion/exclusion criteria evaluation	X	
	Collection of Demographic Information: 
 
• Date of birth
 
• Vital status: dead/alive/unknown
 
• Gender
 
• Smoking status: Smoker/never smoker/prior smoker at the time of first line treatment
 
• Other relevant carcinogen exposure (e.g. consumption of betel nut)
 
		X
	Collection of Medical Information: 
 
• Date of initial diagnosis of cancer
 
• Stage of disease at diagnosis
 
• Anatomical disease site(s) at diagnosis
 
• Anatomical (organ) disease site(s) (e.g. lung metastases) at the time of first line treatment
 
• Locally advanced/unresectable or metastatic disease at the time of first line treatment
 
• Current stage of disease
 
• Other relevant medical history. Date of prior medical events
 
		X

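### Controls are matched on pathological TNM stage, which some eligible patients cannot have and which does not describe disease extent when first-line PFS starts

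*Combined protocol and SAP*

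**What the plan says.** The section Statistical & Analytical Plan and Methodology sets four matching variables for the primary comparison of first-line PFS. The two groups will be "matched with respect to histological subtype, sex, age (+/-5 years), and pathological tumor-node-metastasis (TNM) stage".

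The strength of the commitment is stated elsewhere. Study Type and Design says "Control subjects will be matched based on the characteristics of the NTRK fusion study population to the greatest extent possible". The text after the inclusion criteria says that controls "will be selected in an attempt to closely match NTRK fusion subjects".

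The population is set by Inclusion Criteria, item 3: "Subject has locally advanced/unresectable or metastatic disease". Item 2 admits any solid tumour and gives as examples "soft tissue sarcoma, BRAF wild type melanoma, KRAS wild-type colorectal cancer, central nervous system, EGFR-wild type non-small cell lung cancer".

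Under medical information, the Visit schedule lists "Stage of disease at diagnosis", the current stage, and, as a separate item, "Locally advanced/unresectable or metastatic disease at the time of first line treatment". It also lists the organ sites involved at first-line treatment and, under treatment information, performance status at first line and previous surgery with dates. No item names TNM or says whether stage is pathological or clinical.

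**The concern.** Matching here is meant to make the groups alike in prognosis at the moment PFS starts to run, so that a difference can be read as the effect of the fusion. The stage-related variable does not do that job, for two reasons.

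- **Availability.** A patient who presents with unresectable or metastatic disease generally has no resection specimen to stage, and TNM does not generally apply to primary CNS tumours. The plan has no rule for these patients. Someone must decide case by case whether to drop the variable, substitute another stage or give up the match. The study is retrospective, so PFS may already be known when that choice is made.
- **Timing.** A patient who does have a pathological stage got it at an earlier operation. Two patients resected at the same stage can begin first-line therapy with different disease, one metastatic and one locally unresectable, and still count as matched.

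The timing problem does not depend on how many patients lack a pathological stage. What is at stake is confounding of the primary comparison by disease extent.

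**Working it through.** The plan gives no figure to reproduce: it has no sample size calculation, fusion frequency, matching ratio or share of patients with a pathological stage. The main check is to set the sections side by side.

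**1. What each candidate variable describes**

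| Variable | Where it appears | Time it describes | Can every eligible patient have it? |
|---|---|---|---|
| Pathological TNM | Matching rule; not named in the data list | Earlier operation | No: needs a specimen and a TNM-staged tumour |
| Stage at diagnosis | Data list; system and basis not stated | Diagnosis | Depends on the system used |
| Current stage | Data list; system and basis not stated | Data collection | Depends on the system used |
| Locally advanced/unresectable or metastatic at first line | Data list; not in the matching rule | Start of first-line therapy | Yes: inclusion item 3 requires one or the other |

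The primary outcome is PFS on first-line therapy. I take its origin to be the start of that therapy. Only the last row describes disease at that time, and it is not a matching variable.

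**2. Is the imbalance dealt with later?** The named test is a log-rank comparison. Cox models are optional, and the covariates to be assessed are not listed. Adjustment for extent is possible but not assured.

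**3. How large could the bias be? (illustration; all inputs assumed)** Let *h* be the hazard ratio for metastatic versus locally advanced disease, and let *p*₁ and *p*₀ be the metastatic shares in the two groups. With no fusion effect, the ratio of average hazards at the start of follow-up is

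(*p*₁*h* + 1 − *p*₁) / (*p*₀*h* + 1 − *p*₀)

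- *h* = 1.5, 60% versus 40%: (0.6 × 1.5 + 0.4) / (0.4 × 1.5 + 0.6) = 1.3/1.2 = 1.08.
- *h* = 2, 70% versus 30%: (0.7 × 2 + 0.3) / (0.3 × 2 + 0.7) = 1.7/1.3 = 1.31.

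For comparison, the plan calls an increase in median of more than 30% clinically relevant, whatever the width of the confidence interval. Under exponential survival that is a hazard ratio of 1/1.3 = 0.77, or 1.30 with the groups reversed. The first case falls well short of that mark; the second reaches it. The direction depends on which group has more metastatic disease.

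**4. How many fusion patients could lack a pathological stage? (illustration; all inputs assumed)** With 7 to 40 fusion patients and 40% to 80% of them lacking it, the number is between 0.4 × 7 = 2.8 and 0.8 × 40 = 32. The range is too wide to be an estimate. It shows only that the documents cannot settle the question.

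**The case against.** The strongest reply is that matching is declared to be best effort in two places. A reader might infer from the matching rule that fusion patients without a pathological stage have no valid control and leave the primary analysis. The documents do not support that. Nothing prescribes exclusion. The criteria for evaluable cases require only first-line outcome information and IHC-tested material. The interim reports are to assess whether a matched comparison is feasible at all. This stands, and patient loss is not part of the point.

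A reader might also infer that pathological TNM is not collected. That goes too far: either stage item could hold it, and surgery is recorded. The accurate statement is that the staging system and its basis are not specified.

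Nor do the documents show that most patients lack a pathological stage. The statistical section speaks of recurrent as well as metastatic disease, so patients who relapsed after surgery are expected and may have one. Only *some* lack it.

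On size, 1.08 is small beside the sampling error of a comparison with few fusion patients, and matching on histology may narrow the imbalance in extent. Both are fair. But a shift in the point estimate is not excused by imprecision when the relevance rule ignores the confidence interval.

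Finally, a two-level extent variable is coarse. It does not grade disease within the metastatic group, and it balances little where nearly all patients with a given histology fall in one category. That is a real limit of the remedy, but not a reason to keep a variable tied to the wrong time.

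**Conclusion.** The concern holds in a limited form. The stated rule matches on a variable that is unavailable or inapplicable for some eligible patients and that, where present, describes an earlier point in the disease. It therefore does not balance disease extent at the start of first-line therapy, although that extent is already on the data list, and no later adjustment for it is guaranteed.

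Best-effort wording removes the threat of prescribed exclusions. It does not correct the timing, and it leaves the handling of missing or inapplicable stage to case-by-case choice.

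The size is unknown. The hazard ratios of 1.08 and 1.31 rest wholly on assumed prognostic effects and imbalances. The conclusion itself needs only two premises: that PFS runs from the start of first-line therapy, and that a pathological stage requires a surgical specimen. The change is worth making before controls are selected.

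**What to change.** In Statistical & Analytical Plan and Methodology, replace pathological TNM as the stage-related matching variable with disease extent at the start of first-line systemic therapy, in two categories: locally advanced/unresectable versus metastatic. Keep histological subtype, sex and age as they are.

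Add one sentence: stage at diagnosis, where available and applicable, will be described by group and may serve as a secondary tie-breaker among otherwise eligible controls; a missing or inapplicable TNM stage never excludes a fusion patient.

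The cost is a line or two of wording and no new data item. The downside is a coarser matching category than TNM for patients who do have a pathological stage; the tie-breaker recovers part of that information.

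### The PFS comparison matches on histology but does not carry the matching into the analysis, and no NTRK hazard ratio adjusted for the collected performance status and disease extent is defined

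*Combined protocol and SAP*

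**What the plan says.** The Statistical & Analytical Plan and Methodology section sets a significance aim, "to determine if there are statistically significant differences in PFS to first line systemic therapy", within a study that it calls descriptive. Its provisions for the comparison are:

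- **Matching:** "The two groups will be matched with respect to histological subtype, sex, age (+/-5 years), and pathological tumor-node-metastasis (TNM) stage". Study Type and Design makes this best effort: "Control subjects will be matched based on the characteristics of the NTRK fusion study population to the greatest extent possible".
- **Test:** "A nonparametric test, such as the log-rank test, based on the Kaplan-Meier estimator for survival curves, will be employed". Strata and matched sets are not mentioned.
- **Model:** predictive modelling, "including Cox proportional hazards models with NTRK fusion as a predictor may also be used". No adjustment set is listed.
- **Covariates:** "An assessment of the impact of certain covariates will be conducted by comparing their associated hazard ratios". They are not named.
- **Relevance rule:** "Clinically relevant changes will be defined as increases in median survival times that are greater than 30%, regardless of confidence interval width".
- **Size:** "the sample size for this study will not be driven by powering the study".

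The Visit schedule lists performance status at first-line therapy, and whether disease was locally advanced or metastatic at that time. The Interim Analyses section makes the matched comparison depend on how many fusions are found.

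**The concern.** The cohort spans sarcoma, melanoma, colorectal, CNS, lung and other tumours, whose first-line PFS may differ a good deal. Histology is used to choose controls, but nothing says that it enters the test. A plain log-rank test would ignore it.

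Separately, matching does not cover performance status at all. It covers disease extent only through TNM stage, which the plan does not date; the Visit schedule lists stage at diagnosis and current stage apart from extent at first-line start. The covariate assessment looks at the covariates' own hazard ratios and is not tied to an adjusted NTRK effect. Two things are at stake: power that few fusion patients can ill afford to lose, and an NTRK hazard ratio that a prognostic imbalance could move.

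**Working it through.** **1. Inputs.** The plan has no power figure to reproduce: it states that no sample size was calculated and gives no alpha, fusion count, control ratio or PFS by histology. Its one effect size is the 30% increase in median; with exponential PFS this is HR = 1/1.3 = 0.769. All else here is assumed: 10, 20 or 40 fusion patients (0.27%, 0.54% and 1.08% of 3,700); five equally common tumour groups, matched exactly; exponential PFS; censoring uniform over 12 to 60 months; two-sided 5%. Control medians in months are wide (3, 6, 9, 12, 24), mild (4, 6, 8, 10, 12) or no spread (8 throughout).

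**2. Test.** Within stratum h, U_h = Σ(d₁ − d·n₁/n) over event times, with variance V_h, and Z = ΣU_h/√ΣV_h. The unstratified test treats all patients as one stratum.

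**3. Power, unstratified v stratified (%), 10,000 replicates.**

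| HR | Spread | Ratio | 10 | 20 | 40 |
|---|---|---|---|---|---|
| 0.5 | wide | 1:4 | 20.2 v 30.9 | 44.5 v 60.1 | 78.9 v 90.3 |
| 0.5 | wide | 1:1 | 15.8 v 19.8 | 31.5 v 41.9 | 57.3 v 72.0 |
| 0.5 | mild | 1:4 | 32.0 v 32.5 | 60.1 v 63.5 | 90.8 v 92.5 |
| 0.5 | mild | 1:1 | 23.6 v 20.6 | 43.7 v 42.8 | 73.8 v 76.0 |
| 0.5 | none | 1:4 | 37.6 v 32.9 | 67.4 v 63.5 | 93.7 v 92.1 |
| 0.5 | none | 1:1 | 28.0 v 21.4 | 49.5 v 43.1 | 79.8 v 75.4 |
| 0.769 | wide | 1:4 | 3.9 v 8.4 | 6.6 v 13.4 | 12.8 v 24.5 |
| 0.769 | mild | 1:4 | 7.0 v 8.9 | 11.5 v 13.8 | 21.4 v 26.0 |
| 0.769 | none | 1:4 | 9.4 v 8.5 | 14.8 v 13.6 | 27.2 v 25.8 |

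With no effect and wide spread, the unstratified test rejects 2.6–3.1% of the time and the stratified test 4.9–5.7%. Matching fixes the tumour mix, so the group difference varies less than the unstratified variance presumes; the test is conservative.

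The unstratified estimate also shrinks. With a true HR of 0.50, the large-sample Cox estimate is 0.58 under wide and 0.53 under mild spread. A second set-up (four histologies with medians 3, 6, 12 and 24; 37 fusion patients; 1:3; no censoring) shows the same pattern: HR 0.60 unstratified against 0.50 stratified, power 78% against 92%.

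**4. Sensitivity (wide, 1:4, HR 0.5, 20 patients).** If 60% of fusions fall in one tumour group, power is 55% v 65%; if 80% do, 63% v 68%. Three strata of similar PFS keep the gain (58.9%). Three strata mixing short and long PFS lose it (46.1%, against 44.2% with none in that run).

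**5. Imbalance with no NTRK effect.** Take poor performance status in 15% of fusion patients and 30% of controls, at HR 2.

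- The hazard ratio at time zero is (0.85 + 0.15×2)/(0.70 + 0.30×2) = 1.15/1.30 = 0.885. It drifts toward 1 as poor-status patients progress first, and the Cox estimate settles at 0.92–0.93. The reverse imbalance gives 1.06–1.09.
- For the medians, put y = e^(−x), with x the time scaled by the good-status hazard. Fusion: 0.15y² + 0.85y = 0.5, so y = 0.537 and x = 0.621. Controls: 0.30y² + 0.70y = 0.5, so y = 0.573 and x = 0.556. The ratio is 0.621/0.556 = 1.12.
- Metastatic disease in 60% v 80% at HR 1.5 gives 0.92–0.95; reversed, 1.06–1.11.
- Performance-status extremes: 20% v 30% at HR 1.5 gives HR 0.96 and median ratio 1.04. 10% v 40% at HR 2.5 gives HR 0.82 and median ratio 1.35, past the plan's 30% line.

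With histology strata and both covariates in the Cox model, the null estimate returns to 0.98–1.02.

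**The case against.** The case for leaving the plan alone is substantial.

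- **Histology is not ignored.** It is a matching factor, and the wording of the test permits a stratified log-rank. A reader might infer that an unstratified test would be invalid or give false positives. The documents do not support that: if matching succeeds, the loss is efficiency only. Confounding by tumour type would return only where best-effort matching fails.
- **Covariates are not excluded.** A reader might infer that the plan rules out adjustment. It does not: it commits to a covariate assessment from a Cox or parametric model, and a multivariable model containing NTRK is a natural reading. What is missing is the covariate list and a defined adjusted NTRK effect.
- **The gain depends on assumptions.** It needs wide PFS differences, spread-out fusions and sensible grouping. At 1:1 with mild spread, stratifying loses 3.0 and 0.9 points with 10 and 20 patients and gains 2.2 with 40.
- **The confounding is modest.** A shift to 0.92 is small beside confidence intervals at HR 0.77 whose upper limit is about 5.7, 3.1 and 2.2 times the lower with 10, 20 and 40 patients. Under the 15% v 30% imbalance, null rejection is at most 5.8% unstratified and 7.1% stratified.
- **The study is descriptive**, conditional on feasibility and openly not powered.

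All of this stands and limits the weight of the point. It does not remove it: if the comparison goes ahead it is the primary objective, and the choices left open could be made after outcomes are seen. The unstated control-to-fusion ratio is missing detail, not a flaw in the analysis.

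**Conclusion.** The point holds as a cheap improvement. The named analysis does not carry the matching through, and collected performance status and disease extent play no stated part in the NTRK estimate.

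The clearer gap is performance status, which is neither matched nor named. A plausible imbalance moves the NTRK hazard ratio by roughly 4–10% in either direction; only a severe one crosses the 30% median rule. The documents give no sign that an imbalance exists, so this is a risk and not a demonstrated bias.

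The histology limb concerns efficiency: about 16 points of power with 20 fusion patients at HR 0.5, 1:4 and wide spread, about 3 with mild spread, and a loss of 4–7 points at 1:1 with no spread. A reader might infer that stratifying would make the comparison adequately powered. It would not: at HR 0.77, power stays at or below about 27% with up to 40 fusion patients. The fusion count remains the main limit, as the plan accepts.

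**What to change.** In Statistical & Analytical Plan and Methodology, for use if the comparison goes ahead:

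1. Report as the main NTRK estimate the hazard ratio with 95% CI from a Cox model stratified by pre-specified histology groups and adjusted for performance status and locally advanced versus metastatic disease at first-line start.
2. Test with the log-rank stratified by the same groups, and show the unstratified log-rank as a sensitivity analysis. The stratified test does not correct for the two covariates, so read it beside the Cox estimate.
3. Fix the groups (by expected PFS), the two covariates and a rule for missing performance status before NTRK status is linked to PFS.
4. State that Kaplan-Meier medians, and so the 30% rule, are not corrected for these imbalances and must be read beside the adjusted hazard ratio.

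The cost is SAP wording and a few lines of code; both covariates are already collected. Histologies must be grouped, and the documents give no PFS by histology to guide this; grouping unrelated to PFS gains almost nothing. If tumour types do not differ, stratifying costs 2–5 points of power at 1:4 and 4–7 at 1:1 (HR 0.5). With 10 fusion patients the two-covariate model is slightly anti-conservative (null rejection 5.7–6.6%).
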